8.1.4 National Early Warning Score (NEWS)

NEWS has demonstrated an ability to discriminate participants at risk of poor outcomes. (Smith, 2016). This score is based on 7 clinical parameters (see [Table 1](#)). The NEWS is being used as an efficacy measure. This should be evaluated at the first assessment of a given study day and prior to administration of study product. The 7 parameters can be obtained from the hospital chart using the last measurement prior to the time of assessment and a numeric score given for each parameter (e.g., a RR of 9 is one point, oxygen saturation of 92 is two points). This is recorded for the day obtained. i.e., on Day 3, Day 3 score is obtained and recorded as Day 3.

Table 1: National Early Warning Score (NEWS)

PHYSIOLOGICAL PARAMETERS	3	2	1	0	1	2	3
Respiration Rate	≤8		9 - 11	12 - 20		21 - 24	≥25
Oxygen Saturations	≤91	92 - 93	94 - 95	≥96			
Any Supplemental Oxygen		Yes		No			
Temperature	≤35.0		35.1 - 36.0	36.1 - 38.0	38.1 - 39.0	≥39.1	
Systolic BP	≤90	91 - 100	101 - 110	111 - 219			≥220
Heart Rate	≤40		41 - 50	51 - 90	91 - 110	111 - 130	≥131
Level of Consciousness				A			V, P, or U

Level of consciousness = alert (A), and arousable only to voice (V) or pain (P), and unresponsive (U).

8.2 Exploratory Assessments

8.2.1 Virologic and Serologic Assays

OP swabs or ET samples and blood will be collected on Day 1, 3, 5, 8, 11, and 15 and stored as outlined in the MOP. Blood samples will be collected on Day 1, 3, 8, 15, 29 and Day 60 visit. The assays used to detect and characterize virologic and immune responses are in development or experimental in nature. Therefore, while viral and immunologic responses to convalescent plasma therapy are thought to be an important endpoint, considering the limitations above, they are listed as exploratory endpoints.

8.2.2 Alternative Ordinal Scales

Given the limited clinical data available for COVID-19, the best construct of ordinal scale is not known. Additional data may be used to construct different ordinal scales to test their utility in a treatment study. These are hypothesis generating and will not be submitted as part of a final CSR.

8.3 Safety and Other Assessments

Study procedures are specified in the SOA. A study physician licensed to make medical diagnoses and listed on the 1572 will be responsible for all trial-related medical decisions.

- Physical examination: A symptom-directed (targeted) physical examination will be performed at screening and when needed to evaluate possible adverse event(s) (i.e. any new symptoms). No physical exam is needed for routine study visits.
- Clinical laboratory evaluations:
 - Fasting is not required before collection of laboratory samples.
 - Blood will be collected at the time points indicated in the SOA. Clinical laboratory parameters include WBC, differential, Hgb, PLT, Creatinine, glucose, total bilirubin, AST, ALT, and PT.
 - This testing will be performed at each clinical trial site in real time.

Table 2: Venipuncture Volumes¹

	Screen	Baseline							
Day +/- Window	-1 to 1	-1 to 1	3±1	5±1	8±1	11±1	15±2	29±2	60±5
Type and screen	X 10 mL								
Safety hematology, chemistry, liver tests		X 10 mL	X 10 mL	X 10 mL	X 10 mL	X 10 mL	X 10 mL	X 10 mL	
Blood for plasma/serum and cells, including research assays		X 32 mls	X 32 mL		X 32 mL		X 32 mL	X 24 mL	X 32 mL

Total volume	10 mL	42 mL	42 mL	10 mL	34 mL	10 mL	42 mL	34 mL	32 mL
Total volume all study days									264 mL

1 See SOE for specific tests to be performed.

2 Total volume calculated assumes no routine clinical laboratory results that can be used for the screening, baseline, and safety laboratory values.

3 Samples may be collected for up to 90 days following the Day 60 visit.

8.3.1 *Procedures to be Followed in the Event of Abnormal Laboratory Test Values or Abnormal Clinical Findings*

If a physiologic parameter (e.g., vital signs, or laboratory value) is outside of the protocol- specified range, then the measurement may be repeated once if, in the judgment of the investigator, the abnormality is the result of an acute, short-term, rapidly reversible condition or was an error. A physiologic parameter may also be repeated if there is a technical problem with the measurement caused by malfunctioning or an inappropriate measuring device (i.e., inappropriate-sized BP cuff).

8.4 Adverse Events and Serious Adverse Events

8.4.1 *Definition of Adverse Events (AE)*

AE means any untoward medical occurrence associated with the use of an intervention in humans, whether or not considered intervention-related. An AE can therefore be any unfavorable and unintended sign (including an abnormal laboratory finding), symptom, or disease temporally associated with the use of medicinal (investigational) product.

Any medical condition that is present at the time that the participant is screened will be considered as baseline and not reported as an AE. However, if the severity of any pre-existing medical condition increases, it should be recorded as an AE.

Given the nature of severity of the underlying illness, participants will have many symptoms and abnormalities in vital signs and laboratory values. All Grade 3 and 4 AEs will be captured as AEs in this trial.

8.4.2 *Definition of Serious Adverse Events (SAE)*

A SAE is defined as “An AE or suspected adverse reaction is considered serious if, in the view of either the investigator or the Sponsor, it results in any of the following outcomes:

- Death;
- A life-threatening AE;
- Inpatient hospitalization or prolongation of existing hospitalization;
- A persistent or significant incapacity or substantial disruption of the ability to conduct normal life functions; or

- A congenital anomaly/birth defect.

Important medical events that may not result in death, be life-threatening, or require hospitalization may be considered serious when, based upon appropriate medical judgment, they may jeopardize the participant and may require medical or surgical intervention to prevent one of the outcomes listed in this definition. Examples of such medical events include allergic bronchospasm requiring intensive treatment in an emergency room or at home, blood dyscrasias, convulsions that do not result in inpatient hospitalization, or the development of drug dependency or drug abuse.

“Life-threatening” refers to an AE that at occurrence represents an immediate risk of death to a participant. An event that may cause death if it occurs in a more severe form is not considered life-threatening. Similarly, a hospital admission for an elective procedure is not considered a SAE.

All SAEs, as with any AE, will be assessed for severity and relationship to study intervention by the Principal Investigator or qualified sub-investigator and will be recorded on the appropriate CRF.

All SAEs will be followed through resolution or stabilization by the Principal Investigator or qualified sub-investigator.

8.4.3 Classification of an Adverse Event

The determination of seriousness, severity, and causality will be made by the Principal Investigator or qualified sub-Investigator upon medical judgment. Qualified sub-investigator includes but is not limited to physicians, physician assistants, and nurse practitioners.

8.4.3.1 Severity of Event

All AEs and SAEs will be assessed for severity, according to the Division of AIDS (DAIDS) Table for Grading the Severity of Adult and Pediatric Adverse Events, version 2.1 (July 2017) (see [Appendix 12.2](#)).

For AEs not included in the protocol defined grading system, the following guidelines will be used to describe severity.

- **Mild (Grade 1):** Events that are usually transient and may require only minimal or no treatment or therapeutic intervention and generally do not interfere with the participant’s usual activities of daily living.
- **Moderate (Grade 2):** Events that are usually alleviated with additional specific therapeutic intervention. The event interferes with usual activities of daily living, causing discomfort but poses no significant or permanent risk of harm to the research participant.
- **Severe (Grade 3):** Events interrupt usual activities of daily living, or significantly affects clinical status, or may require intensive therapeutic intervention. Severe events are usually incapacitating.
- **Severe (Grade 4):** Events that are potentially life threatening.

AEs characterized as intermittent require documentation of onset and duration of each episode. The start and stop dates (duration) of each reported AE will be recorded on the appropriate CRF. Changes in the severity of an AE will be documented to allow an assessment of the duration of the event at each level of intensity.

8.4.3.2 *Relationship to Study Intervention*

For each reported adverse reaction, the PI and Sponsor must assess the relationship of the event to the study product using the following guideline:

All adverse events (AEs) must have their relationship to the study intervention (product, process, and/or procedure) assessed by the clinician who examines and evaluates the participant based on temporal relationship and his/her clinical judgment. The degree of certainty about causality will be graded using the categories below. In a clinical trial, the study product must always be considered.

- Definitely Related – There is clear evidence to suggest a causal relationship, and other possible contributing factors can be ruled out. The clinical event, including an abnormal laboratory test result, occurs in a plausible time relationship to PCCP administration and cannot be explained by concurrent disease or other drugs or chemicals. The response to withdrawal of the PCCP (dechallenge) should be clinically plausible. The event must be pharmacologically or phenomenologically definitive, with use of a satisfactory rechallenge procedure if necessary.
- Probably Related – There is evidence to suggest a causal relationship, and the influence of other factors is unlikely. The clinical event, including an abnormal laboratory test result, occurs within a reasonable time after administration of the PCCP, is unlikely to be attributed to concurrent disease or other drugs or chemicals, and follows a clinically reasonable response on withdrawal (dechallenge). Rechallenge information is not required to fulfill this definition.
- Possibly Related – There is some evidence to suggest a causal relationship (e.g., the event occurred within a reasonable time after administration of the trial medication). However, other factors may have contributed to the event (e.g., the participant's clinical condition, other concomitant events). Although an AE may rate only as "possibly related" soon after discovery, it can be flagged as requiring more information and later be upgraded to "probably related" or "definitely related", as appropriate.
- Unlikely to be related – A clinical event, including an abnormal laboratory test result, whose temporal relationship to PCCP administration makes a causal relationship improbable (e.g., the event did not occur within a reasonable time after administration of the <study intervention> and in which other drugs or chemicals or underlying disease provides plausible explanations (e.g., the participant's clinical condition, other concomitant treatments).
- Unrelated – The AE is completely independent of PCCP administration, and/or evidence exists that the event is definitely related to another etiology. There must be an alternative, definitive etiology documented by the clinician.

8.4.3.3 *Expectedness*

The Principal Investigator will be responsible for determining whether an adverse event (AE) is expected or unexpected. An AE will be considered unexpected if the nature, severity, or frequency of the event is not consistent with the risk information previously described for the study intervention.

8.4.4 **Time Period and Frequency for Event Assessment and Follow-Up**

Safety will be assessed by monitoring and recording potential adverse effects using the Division of AIDS (DAIDS) Table for Grading the Severity of Adult and Pediatric Adverse Events, version 2.1 (July 2017 at each study visit. Participants will be monitored by medical histories, physical examinations, and other studies. If the DAIDS Table for Grading the Severity of Adult and Pediatric Adverse Events, version 2.1 (July 2017) (See [Appendix 12.2](#)) grading does not exist for an adverse event, the severity of mild, moderate, severe, life-threatening, and death, corresponding to Grades 1-5, will be used whenever possible.

At each contact with the participant, the investigator will seek information on adverse events by non-directive questioning and, as appropriate, by examination. Adverse events may also be detected when they are volunteered by the participant during the screening process or between visits, or through physical examination, laboratory test, or other assessments. Information on all adverse events will be recorded in the source documentation. To the extent possible, adverse events will be recorded as a diagnosis and symptoms used to make the diagnosis recorded within the diagnosis event. If the AE is a laboratory abnormality that is part of a clinical condition or syndrome, it should be recorded as the syndrome or diagnosis rather than the individual laboratory abnormality.

As much as possible, each adverse event or follow-up information will be evaluated to determine:

1. Severity grade (DAIDS Table for Grading the Severity of Adult and Pediatric Adverse Events, Corrected version 2.1 (July 2017). See [Appendix 12.2](#).)
2. Duration (start and end dates)
3. Relationship to the study treatment or process – [Reasonable possibility that AE is related: No (unrelated/ not suspected) or Yes (a suspected adverse reaction)]. If yes (suspected) - is the event possibly, probably or definitely related to the investigational treatment?
4. Expectedness to study treatment or process – [Unexpected – if the event severity and/or frequency is not described in the investigator brochure (if applicable) or protocol].
5. Action taken with respect to study or investigational treatment or process (none, dose adjusted, temporarily interrupted, permanently discontinued, unknown, not applicable)
6. Whether medication or therapy taken (no concomitant medication/non-drug therapy, concomitant medication/non-drug therapy)
7. Whether the event is serious

Once an adverse event is detected, it should be followed until its resolution or until it is judged to be permanent, and assessment should be made at each visit (or more frequently, if necessary) of any changes in severity, the suspected relationship to the study treatment, the interventions required to treat it, and the outcome.

For this study, all Grade 3 and 4 AEs, all SAEs occurring from the time the informed consent is signed through the Day 60 visit will be documented, recorded, assessed, and reported. In addition, any grade 1 or 2 or higher hypersensitivity reaction is also reported as an AE.

8.4.5 Adverse Event Reporting

8.4.5.1 Reporting Period

Adverse events will be reported from the time of informed consent until study completion.

8.4.5.2 Investigator Reporting: Notifying the Study Sponsor

Information on all AEs should be recorded on the appropriate CRF.

Every SAE, regardless of suspected causality (e.g., relationship to study product(s) or study procedure(s) or disease progression) must be reported to the sponsor within **24 hours** of learning of its occurrence.

Recurrent episodes, complications, or progression of the initial SAE must be reported to the Sponsor as a follow-up to the original episode within 24 hours of the investigator receiving the follow-up information. A SAE considered completely unrelated to a previously reported one should be reported separately as a new event.

Send the SAE report to the [contact] indicating the protocol number and the study product.

New information regarding the SAE will be reported as it becomes available and in the same manner that the initial SAE (i.e. SAE form). The investigator must follow the event to resolution or until the event is deemed and documented irreversible, whichever is longer.

8.4.5.3 Investigator Reporting: Local Reporting Requirements

The investigator will report AEs and SAEs to the IRB/EC of record and other local regulatory groups per the local requirements.

8.4.6 Serious Adverse Event Reporting

The study clinician will immediately report to the sponsor any serious adverse event, whether or not considered related to the Penn COVID-19 Convalescent Plasma, including those listed in the protocol or investigator brochure and must include an assessment of whether there is a reasonable possibility that the Penn COVID-19 Convalescent Plasma caused the event. Study endpoints that are serious

adverse events (e.g., all-cause mortality) must be reported in accordance with the protocol unless there is evidence suggesting a causal relationship between the Penn COVID-19 Convalescent Plasma and the event (e.g., death from anaphylaxis). In that case, the investigator must immediately report the event to the sponsor.

New information regarding the SAE will be reported as it becomes available and in the same manner that the initial SAE (i.e. SAE form). All serious adverse events (SAEs) will be followed until satisfactory resolution or until the site investigator deems the event to be chronic or the participant is stable. Other supporting documentation of the event may be requested by the study sponsor and should be provided as soon as possible.

The SAE reports to the Sponsor should be sent to: [contact] indicating the protocol number and the study product

The study sponsor will be responsible for notifying the Food and Drug Administration (FDA) of any unexpected fatal or life-threatening suspected adverse reaction per applicable regulations. In addition, the sponsor must notify the FDA, as applicable and all participating investigators of potential serious risks, from clinical trials or any other source, as per the applicable regulation.

A SUSAR is any SAE where a causal relationship with the study product or process or procedure is at least reasonably possible but is not listed in the IB, Package Insert, and/or Summary of Product Characteristics

8.4.7 Reporting Events to Participants

The Sponsor does not plan to report adverse events to participants unless it is required by regulation, the IRB or FDA.

8.4.8 Events of Special Interest

There are no events of special interest in this protocol.

8.4.9 Reporting of Pregnancy

Pregnancy, in and of itself, is not regarded as an AE unless there is suspicion that study drug or process may have interfered with the effectiveness of a contraceptive medication or method. Pregnancy is not a contraindication to receipt of plasma transfusion and will not be reported or followed if not associated to an adverse event.

8.5 Unanticipated Problems

8.5.1 Definition of Unanticipated Problems (UP)

The Office for Human Research Protections (OHRP) considers unanticipated problems involving risks to participants or others to include, in general, any incident, experience, or outcome that meets all the following criteria:

- Unexpected in terms of nature, severity, or frequency given (a) the research procedures that are described in the protocol-related documents, such as the Institutional Review Board (IRB)-approved research protocol and informed consent document; and (b) the characteristics of the participant population being studied;
- Related or possibly related to participation in the research (“possibly related” means there is a reasonable possibility that the incident, experience, or outcome may have been caused by the procedures involved in the research); and
- Suggests that the research places participants or others at a greater risk of harm (including physical, psychological, economic, or social harm) than was previously known or recognized.

UP are generally non-medical events, as medical events would be capture under AEs.

8.5.2 Unanticipated Problem Reporting

Unanticipated problems (UPs) such as:

- Post-marketing withdrawal of a drug, device, or biologic used in a research protocol due to safety concerns.
- FDA ban of a drug, device, or biologic used in a research protocol due to safety concerns.
- Complaint of a participant when the complaint indicates unexpected risks, or the complaint cannot be resolved by the research team
- Breach of confidentiality
- Incarceration of a participant when the research was not previously approved under Subpart C and the investigator believes it is in the best interest of the participant to remain on the study
- Premature closure of a study (e.g., due safety, lack of efficacy, feasibility, financial reasons, etc.) should be reported by the investigator to the Sponsor and the reviewing Institutional Review Board (IRB). The UP report will include the following information:
 - Protocol identifying information: protocol title and number, PI’s name, and the IRB project number;
 - A detailed description of the event, incident, experience, or outcome;
 - An explanation of the basis for determining that the event, incident, experience, or outcome represents an UP;
 - A description of any changes to the protocol or other corrective actions that have been taken or are proposed in response to the UP.

To satisfy the requirement for prompt reporting, UPs will be reported using the following timeline:

- UPs that are serious adverse events (SAEs) will be reported as any other SAE.
- Any other UP will be reported to the Sponsor and IRB within 3 days of the investigator becoming aware of the problem.

8.5.3 Reporting Unanticipated Problems to Participants

The Sponsor does not plan to report adverse events to participants unless it is required by regulation, the IRB or FDA.

9 STATISTICAL CONSIDERATIONS

9.1 Statistical Hypotheses

- **Primary Safety Endpoint:** Cumulative incidence of serious adverse events (SAEs), i.e. the proportion of individuals with at least one SAE, at Day 29.
- We hypothesize that 2 units of convalescent plasma will be safe and will not result in a difference in SAE rates between the experimental and control arms. The analysis will be primarily descriptive summaries by arm. We will calculate the proportion of individuals that experience at least one SAE by arm, along with 95% Clopper Pearson confidence intervals. We expect any related AE to happen relatively shortly after infusion but will assess the AE at all study timepoints. Overall SAE rates, those broken down by system organ class and preferred term will be summarized.
- **Primary Efficacy Endpoint:** Comparison of clinical severity between patients on the experimental versus control arms, determined by the modified 8-point ordinal severity score on Study Day 29. The modified score treats all subjects who have reached levels 1-3 as recovered.
- The key parameter of interest will be the comparison of clinical severity between individuals receiving the experimental intervention versus control, as measured by a clinical severity score that takes into account the modified 8-point ordinal severity score in a prioritized manner. For the modification, recovery will be defined by reaching levels 1-3 on the 8-point ordinal severity score. The null hypothesis is that experimental individuals will have the same median severity as control individuals. The severity score is based on a procedure by Shaw and Fay 2016 [21], which ranks participants based on their Day 29 ordinal severity. All survivors better than non-survivors, individuals with shorter recovery times as better, and individuals with shorter times to death as worse. For individuals who survive but had not yet recovered by Day 29, they will be ranked according to their Day 29 ordinal severity, with individuals achieving the same ordinal severity being ranked according to time to reaching that level of severity. More details are provided in the Statistical Analysis Plan (SAP). This type of severity score, or prioritized outcome, has been advocated in many settings such as infectious disease and cardiovascular outcome settings [22,24,25]. This analysis will have more power to detect differences than looking only at one individual endpoint. Shaw and Fay 2016 showed this test statistic can be interpreted as a weighted average of the log-rank type test statistic for survival and the one for time to recovery amongst survivors. The individual endpoints, time to recovery and time to death, will also be examined as secondary endpoints.
- **Secondary Efficacy Endpoint(s):** Comparison between arms of time to recovery and survival.
- The null hypothesis is that the two arms will have the same recovery time and the same survival time. Kaplan-Meier survival curves will be calculated by arm and compared with a Peto-Peto generalized Wilcoxon test. In the event that deaths occur, the cumulative incidence of recovery will be estimated and compared between groups using Gray's test, which will be able to capture a lower time to recovery due to either a slower event rate or a higher death rate. For interpretive purposes the cause specific hazard ratios for will also be calculated for each event type,

survival and recovery, along with the Peto-Peto test. In the event of no deaths, time to recovery will be summarized with the Kaplan-Meier and compared using the Peto-Peto generalized Wilcoxon test. Analyses of other secondary endpoints listed in Section 3.2 are listed below in Section 9.4.

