9.2 Sample Size Determination

A total of 80 participants are expected to enroll and be randomized in a 1:1 fashion to one of two study arms. Sample sizes are determined by desire to estimate safety and to provide a preliminary idea of efficacy. Given patients will be hospitalized at enrollment, we expect very low missing data rates for early safety and efficacy endpoints. We also expect to be able to have good follow-up post discharge until the end of the study. Patients will be analyzed for safety if they receive at least one dose of the experimental treatment. For efficacy endpoints, analyses will be according to the intent-to-treat principle and outcomes on all enrolled participants will be included for analysis. All power calculations assume Type I error rate of alpha=0.05. Power calculations were done using STATA/SE v16.0.

With a sample size of 40 for a given arm, the expected probability of observing zero or at least one adverse event at varying underlying adverse event rates under a binomial distribution is shown below in Table 3. At this sample size, it is likely to see at least one person with an adverse event even with relatively small rates of adverse reactions. For example, 40 individuals in one arm, there is an 80% chance of observing at least one individual with an event if the underlying AE rate is 4%. The analysis of AE rates will primarily be descriptive due to the lack of power to make formal comparisons with the control arm.

Table 3. Probability of detecting zero individuals or at least one individual with an Adverse Event (AE) for a variety of different underlying AE rates and sample size N =40

AE rate	Pr(0 events)	Pr(1+ event)
0.001	0.96	0.04
0.005	0.82	0.18
0.01	0.67	0.33
0.02	0.45	0.55
0.03	0.30	0.70
0.04	0.20	0.80
0.05	0.13	0.87
0.10	0.01	0.99

While the sample size is driven by safety considerations, we also consider the operating characteristics of the proposed sample size for the analysis of the primary and secondary efficacy endpoints. The primary efficacy outcome is a comparison of the clinical severity score. The severity score is based on

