9.3 Populations for Analyses

- The **safety analysis set** includes all participants who received any amount of the study intervention and for whom post-infusion safety data are available.
- The **per-protocol (PP) analysis set** comprises all participants who completed 1 or 2 unit infusions, have no important protocol deviations, and have valid endpoint data available. These will be documented and tabulated.
- The **intent-to-treat analysis set** includes all participants who were randomized.

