9.4 Statistical Analyses

9.4.1 General Approach

Descriptive statistics (mean, standard deviation, minimum, median interquartile range, and maximum values for continuous variables; and frequencies and percentages for categorical variables) will be computed for all study variables for the above populations. Unless otherwise specified, a complete case analysis will be considered such that missing values will not be replaced, and calculations will be done on available reported values. If there is a substantial amount of missing data we may consider imputation methods and adjust the analyses accordingly. Analyses will primarily be descriptive; estimates will be presented with 95% confidence intervals. Any significance testing will be done at the 0.05 level. Details for the primary and key secondary analyses are provided below. A formal Statistical Analysis Plan (SAP) will be developed prior to performing analyses of the study endpoints.

9.4.2 *Analysis of the Primary Endpoint(s)*

The primary safety endpoint is cumulative incidence of serious adverse events (SAEs) at Day 29, calculated separately by arm as the percent of individuals who had at least one SAE by Day 29. The SAE rate at all other time points of the study will also be calculated. The overall SAE incidence will be presented, as well as separately by system organ class and preferred term groupings. Percentages will be based on the number of participants who were treated (the safety analysis set). Additional frequencies will be presented with respect to maximum severity and to relationship to COVID19 and study product. Multiple occurrences of the same AE will be counted only once according to the highest occurring grade and relationship to study product/COVID19.

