9.4.7 Sub-Group Analyses

Subgroup analyses for the primary and key secondary efficacy outcomes will be considered to see where the differences between the treatment and control groups varied across the following subgroups: age, sex, and duration of symptoms prior to enrollment. A forest plot will display confidence intervals across subgroups. We do not expect to have enough sample size to conduct formal interaction tests to determine whether the effect of treatment varies by subgroup.

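### The primary safety hypothesis compares SAE rates between arms, but the plan names no between-arm estimate or interval for it; the primary severity score also lacks a named effect measure.

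*Combined protocol and SAP*

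**What the plan says.** **Safety.** Section 9.1 hypothesises that two units of plasma will be safe and "will not result in a difference in SAE rates between the experimental and control arms". The analysis is to be mainly descriptive: "We will calculate the proportion of individuals that experience at least one SAE by arm, along with 95% Clopper Pearson confidence intervals". Section 9.4.2 again computes the Day 29 SAE percentage separately by arm, in the safety analysis set. Section 9.2 gives the reason for going no further: "The analysis of AE rates will primarily be descriptive due to the lack of power to make formal comparisons with the control arm".

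Section 9.3 defines that safety set as one that "includes all participants who received any amount of the study intervention and for whom post-infusion safety data are available".

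**Efficacy.** Sections 9.1 and 9.4.2 describe a ranking and a test statistic for the Day 29 severity score, with further detail left to the SAP. The null is equal median severity in 9.1 and a 50-50 chance of lower severity in 9.2. Section 9.4.7 adds, for the primary and key secondary efficacy outcomes: "A forest plot will display confidence intervals across subgroups". It does not say which quantity those intervals describe.

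**The concern.** A statement about a difference between arms needs an estimate of that difference, with its uncertainty. The primary safety analysis supplies two one-sample summaries. Two intervals set side by side tend to be read by whether they overlap, which is a poor guide: they can overlap when the interval for the difference excludes zero. When they overlap widely, they do not show how large an excess the data still allow. In a trial of 40 per arm that allowance is the main thing a reader needs to know, because 9.2 says the sample size was set to estimate safety and to give a preliminary idea of efficacy.

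Low power means that a non-significant test would say little. It does not argue against an interval, which is how a small trial shows what it cannot rule out. A difference with an interval is also compatible with a descriptive analysis, whereas a hypothesis of no difference is not a descriptive statement.

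**Working it through.** **Inputs.** Section 9.2 gives the sample size ("A total of 80 participants are expected to enroll and be randomized in a 1:1 fashion to one of two study arms"), so n = 40 per arm. It also gives the error rate ("All power calculations assume Type I error rate of alpha=0.05"); sidedness is not stated, so two-sided is assumed and z = 1.96. The documents give no expected SAE rate, so 10% to 50% is assumed.

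**The plan's own figures.** Table 3 follows from Pr(1+ event) = 1 − (1 − p)^40. At p = 0.04 this is 1 − 0.96^40 = 0.805, printed as 0.80, and all eight rows reproduce. The power for 0.50 against 0.80 with 40 per arm comes to 0.816, against about 80% stated. There is no arithmetic error. However, Table 3 concerns seeing at least one event in a single arm and says nothing about a difference between arms.

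**Formulas.**
- Clopper-Pearson, per arm with x events: lower limit is the 0.025 quantile of Beta(x, n − x + 1); upper limit is the 0.975 quantile of Beta(x + 1, n − x).
- Wilson limits (l, u): [p + z²/2n ± z√(p(1 − p)/n + z²/4n²)] / (1 + z²/n).
- Newcombe interval for d = p₁ − p₂: lower d − √[(p₁ − l₁)² + (u₂ − p₂)²]; upper d + √[(u₁ − p₁)² + (p₂ − l₂)²].

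**Equal observed rates, 40 per arm.**

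| SAE rate in both arms | Clopper-Pearson, each arm | 95% CI for the difference (points) |
|---|---|---|
| 10% (4/40) | 2.8% to 23.7% | ±14.4 |
| 20% (8/40) | 9.1% to 35.6% | ±17.6 |
| 30% (12/40) | 16.6% to 46.5% | ±19.5 |
| 40% (16/40) | 24.9% to 56.7% | ±20.6 |
| 50% (20/40) | 33.8% to 66.2% | ±20.9 |

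For the 40% row the Wilson limits are 0.2635 and 0.5540, so the half-width is √(0.1365² + 0.1540²) = 0.206. Miettinen-Nurminen limits are within 1 point throughout.

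**Unequal rates: 20/40 against 10/40.** The Clopper-Pearson intervals are 33.8% to 66.2% and 12.7% to 41.2%, which overlap. The Wilson limits are 0.3520 to 0.6480 and 0.1419 to 0.4019, and d = 0.25.
- Lower: 0.25 − √(0.1480² + 0.1519²) = 0.038.
- Upper: 0.25 + √(0.1480² + 0.1081²) = 0.433.

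The difference is 25 points (95% CI 3.8 to 43.3), and Fisher's exact p = 0.037.

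**How often the reading method matters.** Exact enumeration of the two binomials at assumed true rates of 60% and 30%: the two Clopper-Pearson intervals are disjoint in 38% of trials, Fisher's test gives p ≤ 0.05 in 72%, and the Newcombe interval excludes zero in 80%.

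**Severity score.** With no ties and 40 per arm, the null standard error of the win probability is √[(2n + 1)/(12n²)] = √(81/19,200) = 0.065. An observed value of 0.50 would therefore carry a 95% CI of about 0.37 to 0.63 (win odds 0.59 to 1.68).

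**The case against.** The safety analysis is openly descriptive in a phase 1 trial, and nothing in the plan says the arms will be compared by interval overlap. The 38% figure therefore describes a reading the plan might invite, not a procedure it adopts. Section 9.4.3 names Fisher's exact test for binary proportions; against that test the contrast at 60% and 30% is 72% with 80%, much smaller. This stands as a limit on the size of the point. It does not remove the point: Fisher's test appears under secondary endpoints, gives a p-value and no interval, and is not mentioned for the primary SAE proportion.

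A reader might infer that the trial will be unable to say how large a harm remains possible. The documents do not support that, because both proportions will be reported and anyone with the counts can compute the difference interval. The gap is that it is not pre-specified. Nor do they support a prediction that a large excess of SAEs would be passed off as safe. Section 9.4.4 adds tabulations by arm and time point and Kaplan-Meier curves for death and for time to first composite event, and 9.4.6 provides DSMB review.

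A reader might also infer that the severity score will be reported as a test only. That is too strong as well. Section 9.4.1 promises 95% intervals for estimates, 9.4.7 implies an effect estimate, 9.4.3 plans cause-specific hazard ratios for survival and recovery, and the detail is deferred to a SAP that is not in the text reviewed. What stands is that the protocol sections name no effect measure for the score itself: a general rule on intervals does not choose one, and hazard ratios for the components do not summarise the composite.

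**Conclusion.** The point holds as one of pre-specification. The primary safety hypothesis is comparative and the named primary safety analysis is not. With 40 per arm and equal observed SAE rates, differences of about 14 points (at 10%) to 21 points (at 50%) in either direction remain compatible with the data, so wording such as no difference would claim more than the trial can show. These sizes rest on the assumed SAE rates, a two-sided 95% level and full arms of 40.

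There is a linked obstacle. Read literally, the safety set in 9.3 contains no controls, because they receive no study intervention and have no post-infusion data. As defined, it supplies no control denominator for the by-arm percentages, let alone for a difference.

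The missing effect measure for the severity score is a lesser matter and is held with less confidence, because the SAP may supply it.

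**What to change.** 1. In 9.1 and 9.4.2, make the primary safety estimate the risk difference (plasma minus control) in participants with at least one SAE by Day 29, with a 95% Newcombe or Miettinen-Nurminen interval. Keep it descriptive, and keep the per-arm proportions beside it.
2. Replace the no-difference wording in 9.1 with a statement of the largest excess in SAEs that the interval excludes.
3. In 9.3, define the safety set so that it includes control participants, with a stated start of follow-up for them, and bring the matching sentence in 9.2 into line.
4. For the severity score, name the win probability (or win odds) with a 95% CI beside the rank test, use it in the 9.4.7 forest plot, and state one null consistently in 9.1 and 9.2.

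The cost is protocol and SAP wording and a few lines of code, with no change to sample size or data collection. The downside is that the safety conclusion will look less certain, although the information in the data is unchanged.
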